7.4.4. Screen Failures

Minimal data for patients who fail screening such as demographic information and the reason for screen failure will be collected.

Patients that fail to meet eligibility criteria may be re-screened at the discretion of the Medical Monitor. The Medical Monitor will clearly document the rationale for any re-screening decision. Patients that are allowed to re-screen will be assigned a new screening number, re-consented and may have screening assessments repeated if necessary.

7.5. Treatment Administered

7.5.1. Study Medication Treatment Arm(s)

Investigational Medicinal Product Arm:

- FX006: an extended-release formulation of TA in 75:25 PLGA microspheres. Nominal 32 mg TA, administered as a single 5 mL IA injection.

7.5.2. Identity of Investigational Product(s)

FX006 is supplied as a sterile, white to off white powder in a single unit dose 5 mL vial with a butyl rubber stopper, aluminum seal and plastic cap. FX006 is reconstituted in diluent containing an isotonic, sterile aqueous solution of sodium chloride (NaCl; 0.9% w/w), carboxymethylcellulose sodium (CMC; 0.5% w/w) and polysorbate-80 (0.1% w/w) to form a suspension prior to IA injection. Diluent will be supplied as a sterile liquid in a 5 mL vial with a butyl rubber stopper, aluminum seal and plastic cap. FX006 will be reconstituted in 5.0 mL of diluent to form a suspension immediately prior to IA injection. FX006 will be administered as a single 5 mL IA injection.

7.5.3. Receipt, Preparation, Dispensing, and Storage

Study medication will be shipped to the site from the drug supply distribution center. Receipt and dispensation of study medication will be properly documented within the Drug Tracking Module. Any temperature excursions should be documented in the Drug Tracking Module and on specified documents for Sponsor assessment and authorization for continued use.

Dispensing, preparation and administration of investigational products occurs under the supervision of the Principal Investigator or a qualified sub-investigator. The Principal Investigator may only delegate these activities in accordance with state licensing board requirements, local institutional policies, and applicable law. Before delegating this activity, the Principal Investigator should also ensure that the delegate is trained on and understands the requirements of the protocol.

The packaged kits of FX006 will be stored in a secure area and will be stored refrigerated at 2 to 8 °C.

7.5.4. Packaging and Labeling of Study Medication

The packaged kit of FX006 will contain one (1) vial of FX006, one (1) vial of Diluent, and a vial adapter. The FX006 and diluent vials will be labelled with their respective unique lot numbers within the packaged kit, which will be affixed with its own label and kit number.

7.5.5. Return of Study Medication

All study medications (packaged kits/used and unused vials) will be returned to the drug supply distribution center. Return of study medications will be properly documented.

7.5.6. Method of Assigning Patients to Treatment Groups

This is a single arm open-label study. All patients will receive a single IA injection of FX006 32 mg.

7.5.7. Blinding

This is an open-label study.

7.5.8. Study Drug Administration Procedure

IA injections of study drug will be performed by the assigned injector. The injector may choose the position of the knee (e.g., extended or flexed), the approach for the injection (e.g., medial or lateral) and the numbing agent to be used based on standard of care. Sterile technique should be used.

Prior to injection, the index knee should be thoroughly cleansed using a bactericidal solution. The index knee will be aspirated in all cases prior to administration of study medication. Following attempted aspiration, 5 mL of the reconstituted FX006 will be injected into the synovial space. Refer to the Pharmacy Binder for detailed instructions on how to prepare FX006.

The same needle used for synovial fluid aspiration may also be used for IA injection of study drug, thereby allowing for a single injection with syringe replacement. The injector will use a 21 gauge or larger needle for injection and aspiration of fluid.

Injector will record injection procedure and any product related issues relating to reconstitution or administration of FX006 (e.g. inability to achieve an appropriate suspension, inability to administer the full dose due to clogging of the needle) and report the occurrence to the Site Monitor, as detailed in the Pharmacy Binder.

Post-Injection Care

Patients should be advised to avoid strenuous activities or prolonged weight-bearing activities for approximately 24 to 48 hours following the injection and to also maintain a stable lifestyle with regard to physical activity throughout the duration of the study.

If the patient has an immediate reaction (e.g., tenderness, increased pain, swelling, effusion, decreased mobility of the index joint) the patient should be treated according to local clinical guidelines and physician experience. Refer to protocol Section 8.4.3.

7.5.9. Treatment Compliance

Study medication will be administered by the injector in the clinic. Details regarding study medication administration will be documented in the electronic Case Report Form (eCRF). The receipt, dispensation, and return/destruction of any study medication will be properly documented per the instructions within the Drug Tracking Module.

If for any reason the administration of study medication is stopped before the entire volume is injected, the injector should document the reason for stopping administration and record the volume delivered.

7.5.10. Removal of Patients from Therapy or Assessments

Each patient in this study receives study medication as a single IA injection. Therefore, discontinuation from treatment is not applicable. However, each patient may discontinue from the study for further assessments and study visits.

Each patient will be informed of his/her right to discontinue from the study at any time for any reason and without prejudice to alternative treatment. The PI may also discontinue a patient from the study at any time if, for example, he/she considers the patient's health to be compromised by remaining in the study, or the study is prematurely terminated. In these cases, the PI will:

1. Attempt to arrange for a formal Early Termination Visit and complete the study assessments specified for the End-of-Study scheduled for Week 24.
2. Determine whether the patient is willing to be contacted to follow ongoing or new AEs through Week 24 (if reason for discontinuation is not "subject withdrew consent").
3. Document patient consent in the source document for continued follow-up.
4. Contact the patient as necessary (via phone or in-person) to follow ongoing or new AEs through Week 24 (concomitant medications associated with any AE will also be captured).

Data collected from discontinued patients will be included in the clinical study report. Patients who discontinue from the study may be replaced at the discretion of the Sponsor.

7.6. Prior and Concomitant Medications and Therapies

During the study, all existing (prior to study entry), new, or changes in concomitant medications and the associated reasons for use or change will be documented and reported.

7.6.1. Allowable Medications and Therapies

The following medications and therapies may be taken or used throughout the study:

- Any treatment for a pre-existing condition or for an AE, including the study indication (e.g., analgesic medications), that is not listed below as restricted
- Physical therapy for index knee
- Bracing of index knee

7.6.2. Restricted Medications

Per the exclusion criteria, a patient is not eligible for this study if he/she has received any of the indicated treatments within the specified windows detailed in the Exclusion criteria (Section 7.4.3). In addition, the following medications should not be taken or used from the time of obtaining consent to the End of Study visit:

- Topical or oral NSAIDs (from 5 days prior to Pre-treatment MRI through Week 6, and again from 5 days prior to Week 24 MRI)
- IV, IM, or oral corticosteroids
- IA corticosteroids in any joint
- Any IA intervention in index knee including aspiration or the injection of any approved or investigational agent, including viscosupplementation (hyaluronic acid)
- Any investigational drug, device or biologic
- Immunomodulators, immunosuppressives, or chemotherapeutic agents
- Live or attenuated vaccines

7.7. Study Variables

7.7.1. Safety Variables

Safety and tolerability will be evaluated based on AEs spontaneously reported by the patient or discovered by the Investigator and findings from the following assessments: physical examinations, index knee assessments, vital signs, and clinical laboratory evaluations.

7.7.2. Imaging Variables

Synovial volume and structural changes in various tissues (bone, cartilage, meniscus) and change in contrast enhancement of tissues other than synovium will be evaluated on the basis of MRI by a central imaging vendor.

7.7.3. Efficacy Variables

Efficacy will be evaluated on the basis of the results of the WOMAC[®] Osteoarthritis Index LK 3.1, 5-point scale): pain, stiffness and function domains independently and collectively (Bellamy et al, 1988), the KOOS QOL Subscale (<http://www.koos.nu/>) and a set of questions exploring pain and stiffness of the knee.

7.7.4. Biomarker Variables

Synovial fluid samples will be preserved for a maximum of 5 years for potential future analyses of biomarkers that may contribute to the pathogenesis of OA and/or be associated with responsiveness to FX006 treatment. No genomic analyses (gene sequencing studies) will be performed using these samples. Patients will be able to withdraw consent throughout the duration of storage. Once analysis has begun, consent will no longer be able to be withdrawn.

Whole blood samples will be taken from patients at Baseline/Day 1. Total RNA will be isolated from these samples for analysis of messenger RNA (mRNA) levels of the pro-inflammatory cytokine IL-1 β . The expression of baseline IL-1 β among patients will be compared to several other parameters, such as index knee X-rays and MRI images, with the goal of determining if baseline mRNA IL-1 β expression contributes to the pathogenesis of OA and/or is associated with responsiveness to FX006 treatment.

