6.3. Exploratory Objectives

The exploratory objectives of this study are:

- to assess structural changes in bone, cartilage, and meniscus.
- to assess changes in contrast enhancement of tissue other than synovial tissue.
- to identify Responders and Non-Responders by assessing structural and contrast changes in bone, cartilage, and other tissues.
- through assessment of blood IL-1b mRNA levels, to segment patients into inflammatory and non-inflammatory phenotypes, and to examine the response to therapy of these phenotypes.

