7.3.5. Rationale for Control Type

Not applicable. This is a single arm open-label study.

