7.4.2. Inclusion Criteria

To be included in the trial, patients must fulfill the following criteria:

1. Written consent to participate in the study
2. Male or female ≥ 40 years of age
3. Body mass index (BMI) ≤ 40 kg/m²
4. Ambulatory and in good general health
5. Willing and able to comply with the study procedures and visit schedules and able to follow verbal and written instructions
6. Willing to abstain from use of the following protocol-restricted medications during the study:
 - Topical or oral NSAIDs (from 5 days prior to Pre-treatment MRI through Week 6, and again from 5 days prior to Week 24 MRI)
 - Intravenous (IV), intramuscular (IM) and oral corticosteroids (Note: inhaled, intranasal, and topical corticosteroids are allowed)
 - IA corticosteroids in any joint (other than the study medication)
 - Any IA intervention in the index knee including aspiration or the injection of any approved or investigational agent, including viscosupplementation (hyaluronic acid)
 - Any investigational drug, device or biologic
 - Immunomodulators, immunosuppressives, or chemotherapeutic agents
 - Live or attenuated vaccines
7. Symptoms consistent with OA of the index knee for ≥ 6 months prior to Screening (patient self-report is acceptable)

8. Currently meets ACR Criteria (clinical and radiological) for OA ([Altman et al, 1989](#)) as follows:
 - Knee pain
 - at least 1 of the following:
 - Age > 50 years
 - Stiffness < 30 minutes
 - Crepitus
 - Osteophytes (as determined by central reading facility of index knee X-ray obtained at Screening)
9. Kellgren-Lawrence (K-L) Grade 2 or 3 in the index knee based on X-ray performed during Screening (centrally read)
 - a) Grade 2: definite osteophytes and possible narrowing of joint space
 - b) Grade 3: moderate multiple osteophytes, definite narrowing of joint space and some sclerosis and possible deformity of bone ends
10. WOMAC A total sum score of ≥ 6 at Screening and Baseline/Day 1
11. Index knee pain on most days over the last month (as reported by the patient)
12. If bilateral OA exists, pain in the contralateral knee must be less than pain in the index knee as reported by the patient; if pain is equal, index knee will be identified based on knee with highest level of inflammation as determined by ultrasound

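### The IL-1β plan sets a pathogenesis goal that one treated, OA-only arm cannot reach, and its two-phenotype response objective gives up information that a continuous analysis would keep

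*Protocol*

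**What the plan says.** The protocol makes two separate statements about IL-1β.

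- **The biomarker goal** (Section 7.7.4, repeated in the synopsis under Biomarker Variables). Expression "among patients will be compared to several other parameters, such as index knee X-rays and MRI images", in order to determine whether it "contributes to the pathogenesis of OA and/or is associated with responsiveness to FX006 treatment". No grouping of patients is mentioned there.
- **The phenotype objective** (Section 6.3, repeated in the synopsis under Objectives). Blood IL-1β mRNA levels are used "to segment patients into inflammatory and non-inflammatory phenotypes, and to examine the response to therapy of these phenotypes". This stands in the list headed "The exploratory objectives of this study are".

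The design behind both is fixed elsewhere in the protocol:

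- Sampling: "Whole blood samples will be taken from patients at Baseline/Day 1" (Section 7.7.4). Table 1 marks the IL-1β sample at that visit only, before dosing.
- Population: each patient "Currently meets ACR Criteria (clinical and radiological) for OA" (Section 7.4.2) and is K-L grade 2 or 3.
- Control: "Not applicable. This is a single arm open-label study" (Section 7.3.5).
- Treatment: "All patients will receive a single IA injection of FX006 32 mg" (Section 7.5.6).

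**The concern.** Determining a contribution to pathogenesis is a causal aim. The design has no OA-free patients, no untreated patients and no second IL-1β measurement. The method given, comparison with X-ray and MRI, yields associations within established, treated disease. A statistical analysis plan cannot close that gap, because it lies between a goal stated in the protocol and the design stated in the same protocol.

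The response question has a related limit. If patients with high IL-1β change more after injection than patients with low IL-1β, the marker may be modifying the drug effect, or it may be predicting how the knee would have changed anyway. Entry requires a WOMAC A sum of at least 6, and the Synovitis Imaging Population requires more than 3000 mm³ of synovial volume, so some regression to the mean is to be expected. A marker that tracks baseline severity could then look like a predictor of response.

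The phenotype objective also reduces a measured level to two classes, which costs precision in a study of about 100 patients. At stake is how the biomarker results are described, and whether a modest real association would be seen.

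**Working it through.** The protocol gives no effect size, power or cut-off for the biomarker analysis, so there is no figure to reproduce. The check has three parts.

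**1. Goal against design**

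| What the goal would need | What the protocol provides |
|---|---|
| Contrast with people without OA, or marker measured before disease | OA patients only, K-L grade 2 or 3 |
| Untreated course of structural change | All patients injected on Day 1 |
| Marker change set against disease change | One pre-dose sample |
| Drug effect compared across marker levels | No control arm |

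What remains estimable is the cross-sectional association with baseline X-ray and MRI findings, and the association of the baseline level with change after FX006.

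**2. Prognostic and predictive markers in one treated arm**

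Simulation with n = 70 and 4,000 runs. Change was generated with a correlation of about 0.30 with the marker, either because the marker predicts natural course only or because it modifies the drug effect only.

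| Marker type | Mean r, treated | Runs significant at 5% | Mean r, untreated |
|---|---|---|---|
| Prognostic only | 0.30 | 72% | 0.30 |
| Predictive only | 0.30 | 72% | 0.00 |

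The two differ only in untreated patients, and this trial has none.

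**3. Information lost by a two-group split**

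Inputs from the protocol: at least 70 evaluable Synovitis Imaging patients out of about 100 enrolled (Section 9.3), and two-sided α = 0.05 (Section 9.2). Assumptions: a normally distributed marker (after log transformation if needed) and a true linear correlation r with response of 0.2 to 0.4.

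Relative efficiency of a split at quantile q is φ(z_q)² / [q(1 − q)].

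- Median: 0.3989² / 0.25 = 0.637, so 70 patients count as 44.6 and 100 as 63.7.
- 70/30: 0.576, so 70 count as 40.3.
- 80/20: 0.490, so 70 count as 34.3.

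The median is the most favourable cut, hence at most about 64%.

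Power by Fisher's z is Φ(atanh(r)·√(n − 3) − 1.96). For a split, r is replaced by r·√efficiency. At n = 70 and r = 0.30:

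- Continuous: 0.3095 × 8.185 − 1.96 = 0.573, power 72%.
- Median split: r becomes 0.30 × 0.798 = 0.239; 0.2441 × 8.185 − 1.96 = 0.038, power 52%.

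| n | r | Continuous | Median split |
|---|---|---|---|
| 70 | 0.2 | 38% | 26% |
| 70 | 0.3 | 72% | 52% |
| 70 | 0.4 | 93% | 77% |
| 100 | 0.3 | 86% | 67% |

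Cross-check as a comparison of two means at r = 0.30: expected difference 0.479 SD, within-group SD √(1 − 0.239²) = 0.971, power 54% with 35 per group and 69% with 50 per group. This agrees with the Fisher figures to within about 3 points.

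**The case against.** The case for leaving the text alone has four parts.

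**The responsiveness goal is worded as association.** This stands. The association between a pre-dose marker and change after treatment can be estimated in one arm, and one pre-dose sample is enough for a baseline predictor. A reader might infer that the design cannot address responsiveness at all. The protocol does not support that, because it nowhere claims effect modification. What is missing is a statement that the association is not evidence of it.

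**The split is not the method for the pathogenesis question.** This also stands. A reader might run the two statements together. Section 7.7.4 describes only a comparison with other parameters, and the phenotypes belong to a separate objective about response.

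**The cut-off and the model belong in the statistical analysis plan.** This stands for the cut-off. Section 9.4.3 leaves exploratory analyses to that plan, Section 9.2.4 leaves subgroups to it, and the plan is not at hand. A reader might infer that the cut will be picked after outcomes are known, with inflated false-positive rates. The protocol proposes no such procedure, so no error inflation can be charged to it. Nor does it exclude a continuous analysis. But the objective as written names a two-class segmentation, and that is open to comment.

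**The objective is exploratory.** True, and it sets the severity. It does not rescue the pathogenesis wording, which no choice of analysis can satisfy.

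**Conclusion.** The point holds in two limited parts.

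First, the aim of determining whether IL-1β contributes to OA pathogenesis cannot be met by this design. This follows from the protocol's own text and rests on no numerical assumption. Associations with imaging and with change after FX006 remain estimable. Causation and modification of the drug effect do not.

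Second, examining response through two phenotypes keeps at most about 64% of the information. At n = 70 that is a loss of about 12 to 20 percentage points of power over assumed correlations of 0.2 to 0.4, and at n = 100 with r = 0.3 it is 19 points (86% against 67%). These figures assume a normal marker and a linear relation. The correlations are illustrative and not taken from the protocol, and the loss would differ if a true threshold existed.

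Severity is minor. A reader might infer that the trial's main conclusions are weakened. They are not: the primary endpoint, the listed secondary endpoints, the sample size and the safety analyses do not depend on IL-1β.

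**What to change.** - **Section 7.7.4 and synopsis, Biomarker Variables.** Replace the goal for baseline IL-1β with: is associated with baseline X-ray and MRI findings and with change after FX006. Add one sentence saying that, without a control group, such associations are not evidence that IL-1β modifies the effect of FX006.
- **Section 6.3 and synopsis, Objectives.** Make the main analysis a regression of change on continuous log IL-1β, with the baseline value of the outcome as covariate. Keep any inflammatory versus non-inflammatory grouping as a descriptive display, with its cut fixed before IL-1β is linked to outcomes.

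All four places need the edit so that the synopsis and the body agree. The cost is a weaker stated claim and one extra model. No new samples, visits or patients are needed.

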7.8. Schedule of Study Assessments

A summary of the schedule of study assessments is provided in [Table 1](#). Refer to Section [7.9](#) for details of each assessment.

Table 1: Schedule of Study Assessments

Procedures	Screening ¹	Pre-Treatment ²	Baseline / Day 1	Week 6 ³	Week 12 ^{3,4}	Week 18 ^{3,4}	Week 24 / End of Study ³
Informed consent	X ⁵						
Inclusion/Exclusion Review	X		X ⁶				
Medical History/Update	X		X ⁶				
OA Medical History/Update	X		X ⁶				
Prior Treatment & Medications ⁷	X		X ⁶				
Physical Examination	X						X
Index Knee X-ray ⁸	X						
Index Knee Assessment ⁹	X		X ⁶	X			X
Ultrasound examination of index knee ¹⁰		X					
MRI with contrast of index knee ¹¹		X		X			X
12-Lead ECG	X						
Vital Signs	X		X ⁶				X
Height	X						
Weight and BMI	X						X
Hematology & Chemistry ¹²	X						X
HIV, Hepatitis B/C ¹²	X						
IL-1 β mRNA levels ¹²			X ⁶				
eGFR ^{12,13}	X			X			X
Serum Pregnancy Test ¹⁴	X						
Urine Pregnancy Test ¹⁴			X ⁶				X
WOMAC ¹⁵	X		X ⁶	X	X	X	X
Supplemental pain and stiffness questionnaire ¹⁵			X ⁶	X			X
KOOS QOL ¹⁵			X ⁶	X			X
Index knee aspiration and collection of synovial fluid ⁸			X ⁶				
Treatment administration			X				
AEs & ConMeds ¹⁶						X	
SAEs ¹⁷						X	

¹ Screening may occur up to 28 days prior to Day 1

² The Pre-Treatment visit must be within 10 days of Baseline/Day 1 and once eligibility is confirmed.

³ Visit should be conducted within +/- 7 days from scheduled date

⁴ Via telephone

⁵ Consent must be obtained prior to performing any study-specific procedures

⁶ Complete assessment prior to dosing

⁷ Record any medications received within 30 days prior to the Screening visit

⁸ Standing, fixed flexion PA view, weight bearing X-ray of the index knee will be taken using a standardized knee positioning device. The Screening X-ray will be read centrally for KL grade, the presence of osteophytes and the measurement of joint space width.

⁹ Index knee will be assessed for tenderness, heat/redness, swelling, effusion, and Baker's cyst. New clinically significant findings or findings that worsen from the patient's baseline condition should be recorded as AEs.

¹⁰ Ultrasound must be performed within -10 days prior to Baseline/Day 1 and using a linear transducer and with the knee in a semi-flexed position. Synovial proliferation will be confirmed in a transverse view but measured in a longitudinal view only.

¹¹ MRI must be performed within -10 days prior to Baseline/Day 1 and +/- 7 days of Weeks 6 and 24 and only if eGFR results are \geq 40 mL/min per the central laboratory. MRI images should follow the vendor specific knee sequences as detailed in MRI Acquisition Manual.

¹² Via Central Laboratory

¹³ Must be performed within 30 days prior to Week 6 and Week 24 MRI with contrast.

¹⁴ Conduct for females of childbearing potential only. Serum pregnancy test to be performed via central laboratory at Screening; urine pregnancy test to be performed locally at Baseline/Day 1 and results available prior to dosing.

¹⁵ Patient questionnaires to be completed prior to all other assessments

¹⁶ AEs and Concomitant Medications will be captured from Day 1 (from start of study drug administration) to Week 24/Final Visit

¹⁷ SAEs will be recorded from Informed Consent to the end of participation in the study or Week 24/Final Visit

